1.1.1. Estimands

There are 2 estimands for the study.

Estimand 1, composite estimand:

- Population: Participants with moderate-to-severe Atopic Dermatitis (AD) as defined by the inclusion criteria to reflect the targeted participant population;
- Variable: response based on achieving at least a 4-point improvement in the severity of the PP-NRS4 from baseline at Week 2; for participants who drop out for any reason or use rescue therapy (Section 6.5.2) at any time during the treatment period, the response will be defined as “non-responsive” after that point;

- Interventional effect: Effect of randomized treatment accounting for treatment adherence, rescue therapy, and response; the intercurrent event (drop-out or use of rescue therapy) is captured through the variable definition;
- Population-level summary: differences in proportions of responders between abrocitinib and dupilumab.

Estimand 1 composite estimand is the primary estimand for the primary and key secondary endpoints: PP-NRS4 response at Week 2, EASI-90 at Week 4, and EASI-90 at Week 16. Other binary outcome measures such as response based on PP-NRS4 and EASI-90 at all other scheduled timepoints, EASI-75, and IGA, will follow the same structure.

Estimand 2, hypothetical estimand:

- Population: Participants with moderate-to-severe Atopic Dermatitis (AD) as defined by the inclusion criteria to reflect the targeted participant population;
- Variable: Percent change from baseline in SCORing Atopic Dermatitis (SCORAD) at all scheduled timepoints;
- Interventional effect: Effect of randomized treatment as if all participants maintain their randomized treatment; drop-out for any reason and use of rescue therapy are the intercurrent events; data after dropout or use of rescue therapy at any time during the treatment period will be censored;
- Population-level summary: Difference in least-square means between abrocitinib and dupilumab.
- Percent change from baseline or change from baseline to each specific post baseline scheduled time points in a continuous outcome measure such as the Hospital Anxiety and Depression Scale (HADS), Patient-Oriented Eczema Measure (POEM), Dermatology Life Quality Index (DLQI), and EuroQol Quality of Life 5-Dimension 5-Level Scale (EQ-5D-5L) will follow the same structure as defined for SCORAD.

Primary Objectives	Primary Endpoints
To compare the efficacy of abrocitinib 200 mg once daily (QD) versus dupilumab (as per label guidelines) in adult participants on background topical therapy with moderate to severe atopic dermatitis (AD).	- Response based on achieving at least a 4-point improvement in the severity of Peak Pruritus Numerical Rating Scale (PP-NRS4) from baseline at Week 2. - Response based on achieving the Eczema Area and Severity Index (EASI)-90 ($\geq 90\%$ improvement from baseline) at Week 4.
Key Secondary	

To compare the efficacy of abrocitinib 200 mg once daily versus dupilumab on additional efficacy endpoints in adult participants on background topical therapy with moderate to severe atopic dermatitis (AD).	- Response based on achieving the Eczema Area and Severity Index (EASI)-90 ($\geq 90\%$ improvement from baseline) at Week 16.
--	---

Overall Design:

This is a randomized, double-blind, double-dummy, active controlled, multi-center study to assess the efficacy and safety of abrocitinib 200 mg QD compared with dupilumab (administered per label guidelines) in adult participants on background topical therapy, with moderate to severe AD. The treatment duration is 26 weeks. A total of approximately 600 participants will be enrolled from approximately 220 sites globally. There are primary efficacy assessments at Week 2 and Week 4, and a key secondary efficacy assessment at Week 16. Efficacy and safety endpoints will be assessed throughout the entire study. Participants who complete the study through the Week 26 visit and are deemed eligible may enter the long-term extension (LTE) Study B7451015. A study design schematic is presented in Section 1.2.

After providing informed consent, participants will be assessed for study eligibility at the screening visit. Participants will undergo screening within approximately 28 days prior to randomization. Use of screening procedures exceeding 28 days prior to randomization should be discussed with the Pfizer Medical Monitor.

During the screening period, systemic treatments for AD will be washed out, as applicable, according to eligibility requirements. Eligible participants must have a documented history, within 6 months of the screening visit, of inadequate response to treatment with medicated topical therapy for at least 4 weeks or must have required systemic therapies for control of their disease within the previous year. Eligible participants must meet the eligibility criteria, which includes being dupilumab naïve, at baseline.

In addition, participants must be willing and able to use standardized background topical therapy, as per protocol guidelines, throughout the duration of the study. After Week 4, if medically necessary, participants with intolerable AD symptoms may receive locally-approved rescue therapy, at the investigator's discretion, pursuant to the protocol guidelines (refer to Section 6.5.2).

Participants may be re-screened once if they fail the screening evaluation for reasons related to incidental transitory conditions. Participants for whom screen failure is related to failing the disease severity (including extent of disease) inclusion criterion and who subsequently experience worsening AD, which in the investigator's judgement would make them eligible for participation, may be considered for re-screening. Such cases should be discussed with the Pfizer Medical Monitor (or designee) to determine if re-screening is appropriate.

Participants who continue to meet eligibility criteria at baseline will undergo Day 1 assessments and be randomized in a 1:1 ratio to receive abrocitinib 200 mg QD with dupilumab-matching placebo administered every other week or dupilumab 300 mg administered every other week (with a loading dose of 600 mg at baseline) with abrocitinib-matching placebo administered QD. Investigators, participants, and the sponsor study team will be blinded to treatment group assignment.

The total treatment period is 26 weeks. Participants discontinuing early from treatment, or who are otherwise ineligible for the LTE study, will undergo a 4-week follow-up period (See Section 10.12.3 for UK country-specific requirements).

Disclosure Statement:

This is a Parallel Treatment study with 2 Arms that are double-blind, double-dummy.

Number of Participants:

[figure not shown]
Approximately 600 participants will be randomly assigned to study intervention.

Intervention Groups and Duration:

- Abrocitinib 200 mg (2 x 100 mg tablets) administered orally QD and dupilumab-matching placebo administered by subcutaneous injection every other week (2 injections at baseline; to dummy the loading dose) from Day 1 to Week 26 (the last injection of dupilumab-matching placebo will occur at Week 24).
- Dupilumab 300 mg administered by subcutaneous injection every other week (with a loading dose of 600 mg at baseline) and abrocitinib-matching placebo administered orally QD from Day 1 to Week 26 (the last injection of dupilumab will occur at Week 24).

Data Monitoring Committee: Yes

1.2. Schema

1.3. Schedule of Activities (SoA)

The SoA table provides an overview of the protocol visits and procedures. Refer to the relevant noted sections of the protocol for detailed information on each procedure and assessment required for compliance with the protocol.

The investigator may schedule visits (unplanned visits) in addition to those listed in the SoA table, in order to conduct evaluations or assessments required to protect the well-being of the participant.

Procedure	Screening	Study Intervention Period									EOT / ED Visit	EOS Follow-up Visit (4 weeks after ED/EOT)	Notes
		1	2	3	4	5	6	7	8	9			
Visit		D1	D8	D15	D29	D57	D85	D113	D141	D169	D183	D211	
Study Day		WK0	WK1 Call	WK2	WK4	WK8	WK12	WK16	WK20	WK24 Call	WK26	WK30	
Study Week													
Visit Window (Days)	-28	0	±1	±1	±2	±3	±3	±3	±3	±3	±3	±3	
Enrollment													
Informed consent	X												Refer to Section 10.1.3 in Appendix 1 .
Register participant in IRT system	X												
Inclusion/Exclusion Criteria	X	X											Refer to Section 5.1 and Section 5.2 for Inclusion and Exclusion Criteria, respectively.
Demographics: Medical, Tobacco, Alcohol, and Atopic Dermatitis (AD) Disease Histories	X												Any previous history of intolerance/allergy to any drug, regardless of indication. AD disease history includes collection of AD diagnosis and duration
Review Prior/Concomitant Medications & Treatments	X	X	X	X	X	X	X	X	X	X	X	X	

Procedure	Screening	Study Intervention Period									EOT / ED Visit	EOS Follow-up Visit (4 weeks after ED/EOT)	Notes
		1	2	3	4	5	6	7	8	9			
Visit		D1	D8	D15	D29	D57	D85	D113	D141	D169	D183	D211	
Study Day		WK0	WK1 Call	WK2	WK4	WK8	WK12	WK16	WK20	WK24 Call	WK26	WK30	
Study Week													
Visit Window (Days)	-28	0	±1	±1	±2	±3	±3	±3	±3	±3	±3	±3	
Dispense eDiary and instruct participants on use	X												
Train/check understanding of participants on protocol guidance for background medicated and non-medicated topical therapy and daily recording in eDiary		X	X	X	X	X	X	X	X	X	X		Refer to Section 6.5.1 .
Collect eDiary											X	X	Collect the eDiary at Week 26/EOT for participants who rollover into the B7451015 long-term extension study. Collect the eDiary from all other participants at Week 30/EOS (or at the last visit a participant will have if ED).
Provide Participant Emergency Contact Card	X												
Medical Procedures													
Complete Physical Exam	X	X										X	Refer to Section 8.2.1
Targeted Physical Exam				X	X	X	X	X	X		X		Refer to Section 8.2.1
Vital Signs	X	X		X	X	X	X	X	X		X	X	Refer to Section 8.2.2 . Temperature does not need to be recorded at the Week 8 visit.
Weight	X												Refer to Section 8.2.1
Height	X	X					X		X				Refer to Section 8.2.1
Chest X-ray	X												Refer to Section 8.2.3 .

Procedure	Screening	Study Intervention Period									EOT / ED Visit	EOS Follow-up Visit (4 weeks after ED/EOT)	Notes			
		1	2	3	4	5	6	7	8	9				10		
		Study Day	D1	D8	D15	D29	D57	D85	D113	D141				D169	D183	D211
		Study Week	WK0	WK1 Call	WK2	WK4	WK8	WK12	WK16	WK20				WK24 Call	WK26	WK30
Visit Window (Days)	-28	0	±1	±1	±2	±3	±3	±3	±3	±3	±3	±3				
ECG (12-lead)	X	X									X	X	Refer to Section 8.2.4 .			
Laboratory Assessments																
Refer to Section 8.2.5 and Appendix 2 for more information on clinical safety laboratory assessments.																
Serum Chemistry and Hematology (including Coagulation Panel and additional sample for infection studies)	X	X		X	X	X	X	X	X		X	X	Refer to Section 8.2.6 for the infection studies and Appendix 2 for all tests			
Lipid Panel		X			X	X		X	X		X	X	8-hour fast required.			
High-sensitivity C-Reactive Protein (hsCRP)	X	X		X	X	X	X	X	X		X	X	This assessment will be blinded after the screening visit.			
Urinalysis	X	X		X	X	X	X	X	X		X	X				
Serum FSH or Pregnancy Test	X												Serum pregnancy testing at screening is required for WOCBP. FSH test to be performed at screening to confirm postmenopausal status in female participants who have been amenorrhoeic for at least 12 months.			
Urine Pregnancy Test (conducted at study site)		X		X	X	X	X	X	X		X	X	This test must be performed prior to dosing with study intervention for WOCBP.			
HIV Testing	X												Will be performed for all participants; those who screen positive will be excluded from the study.			
HBV and HCV Testing	X												Refer to Section 8.2.5.1			
HBV DNA reflex testing	X							X			X		Refer to Appendix 2 and Section 8.2.5.1 .			

Procedure	Screening	Study Intervention Period									EOT / ED Visit	EOS Follow-up Visit (4 weeks after ED/EOT)	Notes			
		Visit	2	3	4	5	6	7	8	9				10		
		Study Day	D1	D8	D15	D29	D57	D85	D113	D141				D169	D183	D211
		Study Week	WK0	WK1 Call	WK2	WK4	WK8	WK12	WK16	WK20				WK24 Call	WK26	WK30
Visit Window (Days)	-28	0	±1	±1	±2	±3	±3	±3	±3	±3	±3	±3				
Tuberculosis Test	X												A documented TB test performed within 12 weeks prior to Day 1 (Week 0) is acceptable. Refer to Appendix 2 and Section 8.2.5.2 .			
Lymphocyte Subsets		X		X	X	X	X	X	X		X	X				
Serum Sample for Baseline Infection Study		X											Refer to Section 8.2.6 . and Appendix 2			
Study Intervention Administration (NOTE: should occur at the end of the site visit where applicable).																
Randomization		X														
Oral Drug Dispensing		X			X	X	X	X	X				Refer to Section 6.1.1.1			
Injectable Drug Dispensing		X		X	X	X	X	X	X				Refer to Section 6.1.1.2			
Study Intervention Accountability				X	X	X	X	X	X		X					
Participant Injection Training		X											Refer to Section 6.1.1.2			
Observed Study Intervention Administration		X		X	X	X	X	X	X				Refer to Section 6.1.1.2			
Review eDiary to assess completion		X	X	X	X	X	X	X	X	X	X					
Assess eligibility for B7451015											X		Participants who complete the Week 26 visit will be assessed for eligibility for participation in the long-term extension study B7451015.			
Atopic Dermatitis Clinical Assessments																
Eczema Area and Severity Index (EASI)	X	X		X	X	X	X	X	X		X	X	Refer to Section 8.1.2			

Procedure	Screening	Study Intervention Period									EOT / ED Visit	EOS Follow-up Visit (4 weeks after ED/EOT)	Notes
		1	2	3	4	5	6	7	8	9			
Visit		D1	D8	D15	D29	D57	D85	D113	D141	D169	D183	D211	
Study Day		WK0	WK1 Call	WK2	WK4	WK8	WK12	WK16	WK20	WK24 Call	WK26	WK30	
Study Week													
Visit Window (Days)		-28	0	±1	±1	±2	±3	±3	±3	±3	±3	±3	
Body Surface Area (BSA from EASI)	X	X		X	X	X	X	X	X		X	X	Refer to Section 8.1.2.1
SCORing Atopic Dermatitis (SCORAD)	X	X		X	X	X	X	X	X		X	X	Refer to Section 8.1.3
Investigator's Global Assessment (IGA)	X	X		X	X	X	X	X	X		X	X	Refer to Section 8.1.4
Patient-reported Outcomes													
Peak Pruritus Numerical Rating Scale (PP-NRS)	X-----X	→	→	→	→	→	→	→	→	→	→	X	Refer to Section 8.1.6.1 . PROs must be completed before all other clinical assessments.
Dermatology Life Quality Index (DLQI)		X		X			X	X	X		X	X	Refer to Section 8.1.6.2
EQ-5D-5L		X					X	X			X	X	Refer to Section 8.1.6.3
Healthcare Resource Utilization (HCRU)		X					X				X		Refer to Section 8.1.6.4
Patient-Oriented Eczema Measure (POEM)		X					X	X			X		Refer to Section 8.1.6.5
Hospital Anxiety and Depression Scale (HADS)		X					X	X			X		Refer to Section 8.1.6.6
Medical Outcomes Study (MOS) Sleep Scale		X					X	X			X		Refer to Section 8.1.6.7
Skin Pain NRS		X		X			X	X	X		X		Refer to Section 8.1.6.8
Asthma Control Questionnaire (ACQ)		X					X				X	X	Refer to Section 8.1.6.9 . Given to all participants with a prior diagnosis of asthma.

Procedure	Screening	Study Intervention Period										EOT / ED Visit	EOS Follow-up Visit (4 weeks after ED/EOT)	Notes
		1	2	3	4	5	6	7	8	9	10			
Visit		D1	D8	D15	D29	D57	D85	D113	D141	D169	D183	D211		
Study Day		WK0	WK1 Call	WK2	WK4	WK8	WK12	WK16	WK20	WK24 Call	WK26	WK30		
Study Week														
Visit Window (Days)	-28	0	±1	±1	±2	±3	±3	±3	±3	±3	±3	±3		
Optional Accelerometry														
Accelerometry training/retraining	X	X	X	X			X	X	X		X			Refer to Section 8.1.7
Issue/collect accelerometry devices	X	X		X			X	X	X		X			
Night Time Itch Accelerometry	X-----X	X-----X					X	X	X		X			
Hand Eczema Clinical Assessments														
History, subtype, clinical signs and extent	X													Refer to Section 8.1.8 .
Investigator's global assessment (IGA)	X	X		X	X	X	X	X	X		X	X		
Safety														
C-SSRS	X	X				X	X	X	X		X	X		Refer to Section 8.2.7.1
PHQ-8	X													Refer to Section 8.2.7.2
Serious and non-serious adverse event monitoring	X	X	X	X	X	X	X	X	X	X	X	X		Refer to Appendix 3 .
Contraception Check	X	X	X	X	X	X	X	X	X	X	X	X		Refer to Appendix 4 for contraceptive guidance.
Banked Biospecimens														
Banked Biospecimen for Genetics		X												Required to be collected for all participants (as local regulations and IRBs/ECs allow). Collect a 2 mL blood sample optimized for DNA isolation (Prep D1.5). Refer to Section 8.7.2 .

Procedure	Screening	Study Intervention Period									EOT / ED Visit	EOS Follow-up Visit (4 weeks after ED/EOT)	Notes
		1	2	3	4	5	6	7	8	9			
Visit		D1	D8	D15	D29	D57	D85	D113	D141	D169	D183	D211	
Study Day													
Study Week		WK0	WK1 Call	WK2	WK4	WK8	WK12	WK16	WK20	WK24 Call	WK26	WK30	
Visit Window (Days)	-28	0	±1	±1	±2	±3	±3	±3	±3	±3	±3	±3	
Banked Biospecimens for Biomarkers		X		X									Required to be collected for all participants (as local regulations and IRBs/ECs allow). Collect 4 mL blood sample optimized for biomarkers (Prep B2.5) and isolate serum. Collect a 2.5 mL blood sample optimized for RNA isolation (Prep R1). Refer to Section 8.8.4 .

Abbreviations: → = completed daily; Ab = antibody; ACQ = Asthma Control Questionnaire; BSA = body surface area; C-SSRS = Columbia Suicide Severity Rating Scale; DLQI = Dermatology Life Quality Index; DNA = deoxyribonucleic acid; D=Day; EASI = Eczema Area and Severity Index; ECG = electrocardiogram; EOS=End of Study; EOT = End of Treatment; ED= early discontinuation; EQ-5D-5L = EuroQol Quality of Life 5-Dimension 5-Level Scale; FSH = follicle stimulating hormone; HADS= Hospital Anxiety and Depression Scale; HBsAg = hepatitis B surface antigen; HBsAb = hepatitis B surface antibody; HBcAb = hepatitis B core antibody; HBV =hepatitis b virus; HCRU = Healthcare Resource Utilization; HCV = hepatitis C virus; HIV = human immunodeficiency virus; hsCRP = high-sensitivity C-Reactive Protein; IGA = Investigator’s Global Assessment; IRT = Interactive Response Technology; LLQ = lower limit quantification; PHQ-8 = Patient Health Questionnaire 8 items; PP-NRS = Peak Pruritus Numerical Rating Scale; POEM = Patient-Oriented Eczema Measure; PRO = Patient Reported Outcome; RNA = Ribonucleic acid; SCORAD = SCORing Atopic Dermatitis; WK=Week; WOCBP = women of childbearing potential.

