Participants may be re-screened once if they fail the screening evaluation for reasons related to incidental transitory conditions. Participants for whom screen failure is related to failing the disease severity (including extent of disease) inclusion criterion and who subsequently experience worsening AD, which in the investigator's judgement would make them eligible for participation, may be considered for re-screening. Such cases should be discussed with the Pfizer Medical Monitor (or designee) to determine if re-screening is appropriate.

Participants who continue to meet eligibility criteria at baseline will undergo Day 1 assessments and be randomized in a 1:1 ratio to receive abrocitinib 200 mg QD with dupilumab-matching placebo administered every other week or dupilumab 300 mg administered every other week (with a loading dose of 600 mg at baseline) with abrocitinib -matching placebo administered QD. Investigators, participants, and the sponsor study team will be blinded as to treatment group.

After Week 4, if medically necessary, participants with intolerable AD symptoms may receive locally-approved rescue therapy, at the investigator's discretion, pursuant to the following guidelines (refer to [Section 6.5.2](#)).

The total treatment period is 26 weeks. Participants discontinuing early from treatment, or who are otherwise ineligible for the B7451015 LTE study, will undergo a 4-week follow-up period. At Week 24 in the treatment period, all participants will cease injectable dupilumab or its matching placebo. Administration of abrocitinib 200 mg QD or its matching placebo will continue until Week 26. Efficacy and safety endpoints will be assessed throughout the entire study. Participants who complete the study through the Week 26 visit and are deemed eligible may enter the LTE Study B7451015.

See Section 10.12.3 for United Kingdom (UK) country-specific requirements.

For study estimands, refer to [Section 3.1](#).

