5.1. Inclusion Criteria

Participants are eligible to be included in the study only if all of the following criteria apply:
Age

1. Participants must be 18 years of age or older inclusive, at the time of signing the informed consent.

Type of Participant and Disease Characteristics

2. Participants who meet all of the following atopic dermatitis criteria:
 - Clinical diagnosis of chronic atopic dermatitis (also known as atopic eczema) for at least 6 months prior to Day 1 and has confirmed atopic dermatitis at the screening and baseline visits according to Hanifin and Rajka criteria for AD.²¹ Refer to [Appendix 9](#).
 - Documented recent history (within 6 months before the screening visit) of inadequate response to treatment with medicated topical therapy for AD for at least 4 consecutive weeks, or who have required systemic therapies for control of their disease within the past year. NOTE: Medicated topical therapy is defined as a topical product that contains an active pharmaceutical ingredient indicated for the treatment of AD (irrespective of whether it is an over-the-counter [OTC] or prescribed product).
 - Moderate to severe AD (BSA $\geq 10\%$, IGA ≥ 3 , EASI ≥ 16 , and PP-NRS severity score ≥ 4 on the day of the baseline visit).

Sex

3. Male or Female

Contraceptive use by men or women should be consistent with local regulations regarding the methods of contraception for those participating in clinical studies.

a. Male participants:

No contraceptive measures are required.

b. Female participants:

A female participant is eligible to participate if she is not pregnant or breastfeeding, and at least one of the following conditions applies:

- Is not a woman of childbearing potential (WOCBP) (see definitions below in Section 10.4.3)

OR

- Is a WOCBP and using a contraceptive method that is highly effective (with a failure rate of <1% per year), as described below, during the intervention period and for at least 28 days after the last dose of study intervention, which corresponds to the time needed to eliminate any reproductive safety risk of the study intervention(s). If a highly effective method that is user dependent is chosen, *a second effective method of contraception, as described below, must also be used*. The investigator should evaluate the effectiveness of the contraceptive method in relationship to the first dose of study intervention.

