- Due to the possible need for PPD testing and chest radiograph, screening procedures may be performed over more than 1 visit in the 28 days prior to the Day 1 visit.
- Visit windows are based on Day 1 visit. To assure consistency and reduce variability, all study visits should occur in the morning whenever possible. On days of study visits, participants will receive their dose at the clinic during the visit.
- Participants are required to fast for at least 8 hours prior to all visits that include lipid profile panel testing. During the fasting period, participants should refrain from all food and liquids (water and permitted non-study medications are allowed).
- ECGs will be interpreted by a central reader for all visits where it is performed.
- Urine pregnancy test must be performed prior to dosing with the study intervention for WOCBP through the EOT visit.
- Prior to attending a study visit, participants are allowed to shower and bathe but should not moisturize or apply emollient.
- Participants will be instructed about the use of standardized background topical therapy (refer to [Section 6.5.1](#)).
- Procedures conducted as part of the participant's routine clinical management (eg, blood count) and obtained before signing of the ICF may be utilized for screening or baseline purposes provided the procedures met the protocol-specified criteria and were performed within the time frame defined in the [SoA](#).

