8.3.1. Time Period and Frequency for Collecting AE and SAE Information

The time period for actively eliciting and collecting AEs and SAEs (“active collection period”) for each participant begins from the time the participant provides informed consent, which is obtained before the participant’s participation in the study (ie, before undergoing

any study-related procedure and/or receiving study intervention), through and including a minimum of 28 calendar days; except as indicated below after the last administration of the study intervention.

Follow up by the investigator continues throughout and after the active collection period and until the AE or SAE or its sequelae resolve or stabilize at a level acceptable to the investigator, and Pfizer concurs with that assessment.

For participants who are screen failures, the active collection period ends when screen failure status is determined.

If the participant withdraws from the study and also withdraws consent for the collection of future information, the active collection period ends when consent is withdrawn.

If a participant definitively discontinues or temporarily discontinues study intervention because of an AE or SAE, the AE or SAE must be recorded on the CRF and the SAE reported using the CT SAE Report Form.

Investigators are not obligated to actively seek AEs or SAEs after the participant has concluded study participation. However, if the investigator learns of any SAE, including a death, at any time after a participant has completed the study, and he/she considers the event to be reasonably related to the study intervention, the investigator must promptly report the SAE to Pfizer using the CT SAE Report Form.

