3.6.1. Adverse Events

An adverse event will be considered a Treatment-Emergent Adverse Event (TEAE) if the event started during the effective duration of treatment. All events that start on or after the first dosing day and time / start time, if collected, but before the last dose plus the lag time (28 days) will be flagged as TEAEs. The algorithm will not consider any events that started prior to the first dose date.

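### The end-of-study visit window lets the last scheduled contact fall before day 28 after the last tablet, so no scheduled contact guarantees the 28-day adverse-event period

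*Protocol*

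**What the plan says.** **Schedule.** In the Schedule of Activities (protocol Section 1.3), EOT/ED is D183 (Week 26) and the last column, D211 (Week 30), is the "EOS Follow-up Visit (4 weeks after ED/EOT" visit. Both have a window of ±3 days. The EOS column carries adverse-event monitoring, safety laboratory tests, the urine pregnancy test and the contraception check. Section 8 says "Visit windows are based on Day 1 visit".

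**Last tablet.** Section 4.1: "Administration of abrocitinib 200 mg QD or its matching placebo will continue until Week 26". Section 8 has the dose given in clinic on visit days, but the schedule row for observed administration has no mark at EOT. The last tablet is therefore taken on the EOT day or the day before.

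**The 28-day periods.** Section 8.3.1 has active collection of AEs and SAEs run "through and including a minimum of 28 calendar days; except as indicated below after the last administration of the study intervention". SAP Section 3.6.1 flags events that start on or after first dosing "but before the last dose plus the lag time (28 days) will be flagged as TEAEs". Section 5.1 requires contraception "during the intervention period and for at least 28 days after the last dose of study intervention".

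**After the last visit.** Section 8.3.1 also says: "Investigators are not obligated to actively seek AEs or SAEs after the participant has concluded study participation". Section 4.4 treats a participant as having completed the study once the last visit or last scheduled procedure is done. The only later scheduled contact is the telephone call in Section 10.12.3, at 12 weeks after ED/EOT. It applies to UK women of childbearing potential and concerns contraception.

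**The concern.** The nominal schedule fits the 28-day period exactly, with no slack, and the EOS window extends to both sides of it. An early EOS visit therefore lands inside the period that Section 8.3.1 says must be covered. For anyone not entering the extension study, EOS is normally the last contact. A site could hold EOS at the early edge of its window, close the participant and be fully compliant with the schedule, yet have no planned occasion to ask about the remaining days.

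Treatment-emergent AE and SAE incidence are stated safety endpoints. Their definition assumes observation to 28 days after the last dose, which the visit plan does not secure. The last scheduled pregnancy test and contraception check can likewise precede the end of the contraception period.

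**Working it through.** **Inputs.** EOT target D183 and EOS target D211, each ±3 days (Section 1.3). Window anchor: Day 1 (Section 8), or the actual ED/EOT visit (the EOS column header). Last tablet: EOT day or the day before. Early discontinuers: EOT within 1 week after the last dose (Section 7.3).

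**Step 1: the plan's own figure.** 211 − 183 = 28 days = 4 weeks. The stated interval reproduces.

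**Step 2: permitted range.** Let a be the EOT offset and b the EOS offset, each from −3 to +3. Let c be the number of days from last dose to EOT.

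- Windows counted from Day 1: days from last dose to EOS = (211 + b) − (183 + a) + c = 28 + b − a + c.
- EOS counted from the actual EOT: 28 + b + c.

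| Reading | Range (days after last tablet) | Combinations below 28 |
|---|---|---|
| EOT anchor, last tablet on EOT day (c = 0) | 25 to 31 | 3 of 7 |
| EOT anchor, last tablet the day before (c = 1) | 26 to 32 | 2 of 7 |
| Day 1 anchor, c = 0 | 22 to 34 (208 − 186 to 214 − 180) | 21 of 49 |
| Day 1 anchor, c = 1 | 23 to 35 | 15 of 49 |
| Early discontinuer, EOT anchor, c = 0 to 7 | 25 to 38 | 6 of 56 |

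The last column counts permitted offset combinations. These are not probabilities, because the documents say nothing about how visits spread within their windows.

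**Step 3: size of the shortfall.** Against the 28 days in Section 8.3.1 it is 28 − 25 = 3 or 28 − 26 = 2 days with the EOT anchor, and 28 − 22 = 6 or 28 − 23 = 5 days at the Day 1 extreme. The SAP flag is slightly more forgiving, because it counts onsets before last dose + 28. A visit on day 27 loses almost nothing, one on day 25 leaves days 26 and 27, and one on day 22 leaves days 23 to 27 (5 days).

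**Step 4: the injection.** The last injection is at Week 24 (D169). EOS follows 208 − 169 = 39 to 214 − 169 = 45 days later, so only the tablet matters.

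**Step 5: the one-sided window.** With EOS counted from the actual ED/EOT and b from 0 to +6, the interval is 28 + b + c. This gives 28 to 34 days (c = 0), 29 to 35 (c = 1), and 28 to 41 for early discontinuers (c = 0 to 7). No combination falls below 28.

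**The case against.** The strongest reply is that Section 8.3.1 already sets the minimum, whatever the visit date. The Schedule of Activities calls itself an overview and allows unplanned visits, so a site that stops collecting on day 25 breaches Section 8.3.1. This stands. A reader might infer that the protocol authorises a shorter safety period, and it does not. What remains is narrower: no scheduled contact delivers the requirement, and the same section lifts the duty to seek events once participation has concluded. Section 8.3.3 does not help, because it follows up events already reported.

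Other limits also stand:

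- **22 days is the extreme.** It needs EOT at +3, EOS at −3, counting from Day 1 and a tablet on the EOT day. The EOS column header and Section 10.12.3 both count from ED/EOT, which gives 25 or 26 days. Even so, every reading allows a visit before day 28.
- **No share of early visits can be stated.** It is tempting to turn 3 of 7 or 21 of 49 into a percentage of participants. That needs visits spread evenly over their windows, which nothing in the documents supports.
- **Bias between arms is not shown.** One might argue that early discontinuation differs by arm and so ascertainment does too. But early discontinuers are the less exposed group, because their EOT may come up to a week after the last dose (short in 6 of 56 combinations). Those stopped after a dosing interruption (Section 7.1.1) can be further still from the last dose. Both arms take tablets on the same schedule.
- **Contraception is the participant's obligation.** Section 5.1 does not require a test or check on day 28, so an early EOS visit does not breach it.

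**Conclusion.** The schedule and the 28-day period do not fit together. For participants who do not enter the extension study, chiefly those dosed up to Week 26, the last scheduled contact may come 2 to 3 days short of day 28 if EOS is counted from the actual EOT visit. At the extreme of counting both windows from Day 1, it may be 5 to 6 days short. Late events in those days can go unobserved; it does not follow that they will.

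The effect on event counts is small and efficacy is unaffected. The number of participants not entering the extension is not given, so the number exposed cannot be stated. The conclusion rests on the last tablet being taken on the EOT day or the day before, and on sites using the windows as printed. This is a cheap improvement to the completeness of late safety data and does not threaten the trial's conclusions.

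**What to change.** Reconcile Section 1.3 and the Day 1 sentence in Section 8 with the 28-day period already stated in Sections 5.1 and 8.3.1 and in SAP Section 3.6.1:

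1. Keep EOS at 4 weeks after ED/EOT, and state that it is counted from the actual ED/EOT visit. Exempt EOS from the Day 1 sentence in Section 8.
2. Replace the EOS window of ±3 days with 0 to +6 days. The width stays at seven days.
3. Where an EOS visit has already been held before day 28, complete AE collection by telephone on or after day 28.

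Because EOT falls on or after the last dose, this secures at least 28 days for completers and early discontinuers alike. Anchoring EOS to the last dose instead would conflict with other text. If EOT is 7 days after the last dose, EOS at last dose + 28 would be only 28 − 7 = 21 days after EOT, against the 4-week follow-up in Sections 7.1.1, 7.3 and 10.12.3.

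The cost is one schedule cell and one sentence. Some EOS visits happen a few days later and an occasional telephone call is needed. No visit is added, and the UK call, which is timed from ED/EOT, does not change.
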